4.3. Exclusion criteria

- Current medication use which affects appetite
- Pregnancy (as it may affect appetite)
- Current or historic diagnosed eating disorder
- Currently on a diet

- Dietary restriction:
 - Vegetarian
 - Vegan
 - Gluten-free
 - Sugar-free
 - Dairy/lactose-free
 - Food allergy (e.g. milk, eggs, nut, wheat, fish, etc.)

5. METHODS

5.1. Test meals

The portion-manipulated test meals will consist of a pasta-based dish for lunch (3 cheese pasta), and a dish served with rice for dinner (chilli con carne), see Table 1 for more information about the dishes. The portion sizes are informed by pilot studies, including pilot studies conducted to assess the norm range, with portions in the larger portion size condition from the mid-higher end of the range, and portion sizes in the smaller portion size condition from the lower end of the norm range (see **Appendix A**).

Table 1. Portion sizes for each portion-manipulated dish in g and kcal

	Larger portion size (100%)			Smaller portion size (67%)		
	g	kcal	£	g	kcal	£
Lunch						
3 cheese pasta	563	816	2.46	375	544	1.64
Dinner						
Chili con carne & rice	437	509	0.90	291	339	0.60
Dinner including cheese and vegetables on the side (totals)	557	737	1.24	411	568	0.94

On each study day, all participants will receive the same *ad libitum* breakfast in the lab (initial serving providing 1437 kcal) and the same snack box for consumption away from the lab throughout the day (providing 906 kcal). At lunch, participants will have the opportunity to serve themselves more of the main dish. At dinner, participants will be served their main dish with a side of vegetables and they will also have the opportunity to request seconds of the main dish. After their dinner a dessert buffet with three options will be provided (providing 1528 kcal). Chilled water (500mL) will be served with each in-lab meal. The complete study menu can be found in SEP_portion_size MENU_UPDATED_TL.xlsx.

Participants will be requested 1/ not to consume any additional food apart from the items provided as part of the study, and 2/ drink only tea, coffee, and no calorie drinks (water) as they usually would.

Note for each self-service breakfast meal we will also vary the size of the dishware (smaller vs larger), the results of which will be reported in detail elsewhere. Given evidence to date (e.g. [47,48]), we expect this to have no impact on energy intake at breakfast, and this will be tested in analyses (see analysis plan). Manipulation of dishware size (smaller followed by larger dishware size

vs larger followed by smaller dishware size) will be fully counterbalanced with the order of portion size presentation (smaller followed by larger portions vs larger followed by smaller portions).

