5.2. Measures

5.2.1. Energy intake during test meals (breakfast, lunch, dinner and dessert)

All the foods served in the lab will be weighed before and after breakfast/lunch/dinner/dessert in order to determine how much of each food has been consumed by the participants. Energy intake will be calculated by multiplying the consumed weight of each food by the energy density (kcal/g) provided by the food manufacturer.

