7.2. Variables description

7.2.1. Primary outcome

Daily energy intake i.e., energy (kcal) from breakfast, lunch and dinner (main and dessert) in the lab, from the snack box and any self-reported additional foods consumed, summed to provide daily energy intake.

Secondary outcomes

Hunger and fullness. Each participant will have 12 measures of hunger and fullness: [breakfast, lunch, dinner] x [pre meal, post meal] x [larger portion size, smaller portion size]. Daily hunger and fullness ratings across time will be summarised by calculating the area under the curve (AUC) using the trapezoid function [36].

Physical activity will be operationalised as ‘active minutes’ per day which are logged for activities with a metabolic equivalent (MET) of ≥ 3 .

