7.4. Primary analyses

7.4.1. Confirmatory analyses

To be consistent with previous studies we ran investigating the effect of SEP on intended energy consumption (e.g [45]), the primary measure of SEP used in our primary analysis will be highest educational qualification (binary – lower vs higher).

A mixed ANOVA will be used to test the effect of portion size (categorical: larger, smaller; within-subject), SEP (categorical: lower (\leq A level), higher ($>$ A level), between-subjects), the interaction portion size*SEP on daily energy intake. If the interaction between portion size*SEP is significant the analysis will be stratified by SEP (\leq A level, $>$ A level) and two repeated-measures t-tests will be used to examine the effect of portion size (larger vs smaller) on daily energy intake in the two groups of participants separately. We will not correct for multiple comparisons as we specified a priori hypotheses.

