7.4.2. Sensitivity analyses

Sensitivity analyses will be conducted to examine whether the pattern of results from the main analyses differ after 1/ excluding participants guessing the aims of the study, 2/ excluding outliers on main outcome variables (identified as those with a value $>$ 3SD from condition mean) and influential cases (identified as those with a Cook's distance $>$ 1, indicating a multivariate outlier [37], 3/

substituting SEP measure (highest educational qualification, \leq A level, $>$ A level) with alternative measures of SEP (level of education – composite score, subjective socioeconomic status (1-10), and household income).

The main analyses will also be repeated controlling for any non-SEP based demographic variables (e.g. BMI, age) that significantly differ between the higher vs. lower SEP groups in order to examine if results remain consistent. To examine whether the order that portions are presented impacts the findings, the main analyses will be repeated with an additional 2-level between-subjects factor (portion size order: smaller, larger vs larger, smaller). Finally, the main analyses will be repeated with dishware size as an additional 2-level within-subjects factor (dishware size: smaller vs larger).

We will report whether sensitivity analyses result in deviations from the pattern of significance to the main analyses (i.e., any significant differences between conditions becoming not significant, and vice versa).

Note if $>30\%$ participants guess the study aim we will include aim guessing as a between-subjects factor in ANOVA rather than use listwise removal.

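### The promised test of dishware size on breakfast intake is not in the analysis plan, and the daily-intake re-run that stands in for it cannot support a no-impact statement

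*Combined protocol and SAP*

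**What the plan says.** Section 5.1 introduces dishware size as a second manipulation at the self-service breakfast, fully counterbalanced with portion order, and says its results are ones "the results of which will be reported in detail elsewhere". It then states the expectation for this study, and where it will be checked: "we expect this to have no impact on energy intake at breakfast, and this will be tested in analyses (see analysis plan".

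Section 7 mentions dishware once. Under 7.4.2, "the main analyses will be repeated with dishware size as an additional 2-level within-subjects factor (dishware size: smaller vs larger". The main analyses in 7.4.1 test portion size, SEP and "the interaction portion size*SEP on daily energy intake". Section 7.2.1 defines that outcome as breakfast, lunch, dinner and dessert, plus energy "from the snack box and any self-reported additional foods consumed, summed to provide daily energy intake". The reading rule for all the sensitivity analyses is: "We will report whether sensitivity analyses result in deviations from the pattern of significance to the main analyses". No breakfast-only outcome, interval rule or margin appears in section 7.

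Breakfast intake is nevertheless available on its own. Section 5.2.1 says "All the foods served in the lab will be weighed before and after breakfast/lunch/dinner/dessert".

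**The concern.** The statement in 5.1 concerns breakfast; the analysis it points to concerns the whole day. Two things follow.

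- **Outcome.** A difference at breakfast is mixed with the variation of everything eaten afterwards, and eating less or more later in the day can offset it.
- **Reading rule.** The rule asks whether the portion-size conclusions change. Because dishware order is balanced against portion order, a dishware effect is close to orthogonal to the portion contrasts and would barely move their p-values. Unchanged portion results therefore say almost nothing about dishware.

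In addition, a non-significant test is not evidence of no effect unless it comes with an estimate and an interval. At stake is whether this trial can say that dishware did not matter at breakfast.

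**Working it through.** **1. The plan's own figure (7.6).** Inputs: f = 0.175, within-person correlation ρ = 0.7, m = 2 days, α = 0.05 (taken as two-sided), N = 46. Noncentrality λ = f²·N·m/(1−ρ) = 0.030625 × 46 × 2 / 0.3 = 9.39. Power is 0.850 with 44 or 45 denominator df, so the stated 46 for 85% power reproduces. In paired terms this is a difference of 2f = 0.35 SD of daily intake, or dz = 0.35/√(2(1−0.7)) = 0.35/0.775 = 0.452.

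**2. Breakfast as a share of the food offered (5.1).** Larger-portion day: 1437 + 906 + 816 + 737 + 1528 = 5424 kcal, so breakfast is 1437/5424 = 26.5%. Smaller-portion day: 1437 + 906 + 544 + 568 + 1528 = 4983 kcal, so 28.8%. These are initial amounts offered, not intakes. They show only that most of the day's food lies outside breakfast.

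**3. Power for a dishware effect.** The documents give no SD and no expected dishware effect. Assumptions:
- a breakfast effect of 0.5 breakfast SD;
- ρ = 0.7 for both outcomes (the plan's figure for daily intake);
- k = breakfast SD / daily SD between 0.3 and 0.5;
- no later compensation;
- a paired two-day contrast with N−2 df. Each participant sees only two of the four portion-by-dishware combinations, so this takes the dishware term as fitted in an estimable form.

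Breakfast: dz = 0.5/√0.6 = 0.645. Daily total: dz = 0.645·k. Noncentral-t power:

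| Outcome | N=46 | N=60 |
|---|---|---|
| Breakfast | 99.0% | 99.8% |
| Daily, k = 0.3 | 25% | 31% |
| Daily, k = 0.4 | 40% | 50% |
| Daily, k = 0.5 | 57% | 69% |

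If the breakfast correlation is 0.5 instead of 0.7, dz = 0.5 and breakfast power at N=46 is 91%.

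**4. The same comparison in kcal.** Assumed SDs: daily 400–800 kcal, breakfast 150–300 kcal; ρ = 0.7, N=46.
- 50 kcal effect: 8–19% on the daily total, 30–81% on breakfast.
- 100 kcal effect: 19–57% on the daily total, 81% to over 99% on breakfast.
- 200 kcal effect: 57–99% on the daily total.
- 95% CI half-width: 92–184 kcal on the daily total, 35–69 kcal on breakfast.

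If half of a 100 kcal effect is compensated later, power on the daily total is 9–14% (daily SD 500–700).

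**5. The reading rule.** Simulation at N=46 of the portion and portion × SEP tests, with and without a counterbalanced dishware term, for a true portion effect of zero or dz = 0.452. With the 0.5-SD breakfast effect and k = 0.3–0.5, significance status changed for either test in about 1–4% of trials. With no dishware effect it changed in about 1% or fewer. This figure applies only if the dishware term itself is not read; step 3 applies if it is.

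**The case against.** The strongest reply is that 7.4.2 is not meant to study dishware. It asks whether the portion-size results survive once dishware is in the model, and daily intake is the right outcome for that. Dishware is in no study hypothesis, and its detailed results are to be reported separately, where a breakfast analysis may well exist. All of this stands. It does not close the gap, because 5.1 still sends the reader to this plan for the breakfast test.

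Three stronger readings are tempting, and the documents do not support them.

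- **That a breakfast effect would usually be missed.** This depends on assumed SDs and an assumed effect. In three of the six daily-intake scenarios above, detection is at least as likely as a miss. An effect of the trial's design size on daily intake (0.35 SD) has 85% power at N=46, although with k = 0.3–0.5 that requires a breakfast effect of about 0.35/0.5 = 0.7 to 0.35/0.3 = 1.2 breakfast SD.
- **That dishware would be reported as having no effect.** Section 7.4.2 says only that changes in the pattern of significance will be reported. It does not say how a non-significant dishware term will be worded, and nothing forbids giving its estimate.
- **That the primary result relies on dishware having no effect.** Full counterbalancing keeps an additive dishware effect from biasing the portion and portion × SEP contrasts.

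A formal equivalence margin also goes beyond what 5.1 strictly promises; an estimate with an interval would meet it.

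**Conclusion.** The point holds in a limited form. Section 5.1 promises a test of breakfast intake that section 7 does not contain, and this much needs no assumption. The daily-intake re-run is a sound check on the portion-size results but a weak substitute for the missing test: 25–57% power against 99% at N=46, conditional on the 0.5-SD effect, correlation 0.7, SD ratio 0.3–0.5 and no compensation. Whatever the true SDs, neither a non-significant daily result nor an unchanged pattern of significance can establish no impact at breakfast.

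The harm is confined to the dishware statement. The primary conclusions are not threatened, so this should be corrected but is not critical.

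**What to change.** In 7.4.2, add a paired comparison of breakfast intake, larger minus smaller dishware, adjusted for study day (dishware order), reporting the mean difference in kcal with a confidence interval. State that no material impact will be claimed only if the interval lies within a margin fixed before analysis; otherwise report the estimate and make no such claim. Keep the daily-intake re-run, described as a check on the portion-size results only.

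The margin is needed only if a no-impact claim is wanted. For illustration, take a margin of 0.5 SD of the paired breakfast differences, a 90% interval (two one-sided 5% tests) and no true difference: the claim would be reached with probability 91% at N=46 and 97% at N=60. Stating the margin in kcal requires an SD that the documents do not give, so the sponsor would have to choose a kcal figure or supply one.

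The minimum alternative is to delete the cross-reference in 5.1, leave the breakfast question to the separate report, and make no no-impact statement here.

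The cost is a few lines and one analysis of data already collected. The downside is small: the expected no-impact result may have to be reported as inconclusive.

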5.2. Measures

5.2.1. Energy intake during test meals (breakfast, lunch, dinner and dessert)

All the foods served in the lab will be weighed before and after breakfast/lunch/dinner/dessert in order to determine how much of each food has been consumed by the participants. Energy intake will be calculated by multiplying the consumed weight of each food by the energy density (kcal/g) provided by the food manufacturer.

5.2.2. Energy intake from the snack box

Participants will be asked to take a photo of their snack box before bed and send it to the research team via email or WhatsApp. They will be told that all items must be photographed (e.g. if they have eaten a chocolate bar, the empty wrapper must be photographed). Participants will be asked to return the snack box including all food and wrappers the following day during the washout session. Returned items will be checked against the photo in case any items are missing on return, which can then be clarified with the participant. Energy intake from the snack box will be calculated by multiplying the consumed weight of each food by the energy density (kcal/g) provided by the food manufacturer.

5.2.3. Additional energy intake

Participants will be asked not to eat any food apart from the meals and snacks provided during each testing period. To assess compliance and to more accurately measure total energy intake, participants will be asked to provide details of any extra food and drink (excluding water) they consumed outside of the study, during the washout and final sessions. Participants will be reassured that they will not be penalised for eating additional food, only that we need to keep detailed records of it. To calculate additional energy intake, a researcher will enter the recorded additional food items into intake24, an online dietary assessment tool [26], [27].

5.2.4. Hunger and fullness

Participants will rate their current level of hunger and fullness on visual analog scales ranging from 0 to 100 before and after eating each meal in the lab.

5.2.5. Physical activity

Participants will be asked not to perform any vigorous physical activity during the study days and to keep their level of physical activity identical across all the testing days. To encourage compliance with the protocol and to control for potential variation in physical activity level, participants will wear an activity monitor (Fitbit Zip) continuously during each study day (except while bathing) to assess moderate-vigorous physical activity. Fitbit device estimates of active minutes have been validated against gold standard research-grade physical activity monitoring devices, and Fitbit devices have been demonstrated to have high reliability.

5.2.6. Impulsivity

We will use the 30-item Barratt Impulsiveness Scale to measure self-reported trait impulsivity [28] (APPENDIX B).

5.2.7. Inhibition

A Stroop task will be used to measure inhibition ($\approx 2\text{min.}30\text{sec.}$). In this task, participants are given colour words (e.g. “red”) written in colour and are asked to indicate the colour of the word (not its meaning) by key press as fast as they can without making too many errors. Congruent trials: colour word and the colour it is presented in are the same. Incongruent trials: colour word and the colour it is presented in are not the same. Control trials: coloured rectangles. The task includes 4 colours (red, green, blue, black) \times 3 colour-stimuli congruency (congruent, incongruent, control) \times 7 repetitions = 84 trials randomly sampled.

5.2.8. Portion size appropriateness

Participants will complete a computerised task in which they will be asked to select the portion size they consider appropriate to consume for the test foods (portion-manipulated main dishes: lunch and dinner). Food pictures start at 40 kcal and increase in 40 kcal increments up to 1000 kcal.

5.2.9. Satiety responsiveness

We will use the *satiety responsiveness* subscale of the Adult Eating Behaviour Questionnaire (AEBQ) [29] (**APPENDIX C**).

5.2.10. Plate clearing tendencies

We will use the 5-item plate clearing tendencies measure developed by Robinson and colleagues [49]. Participants rate questions (e.g. “I always tend to clear my plate when eating”) from 1 (Strongly disagree) to 5 (Strongly agree) (**APPENDIX D**).

5.2.11. Perceived food insecurity

Food insecurity is defined as “limited or uncertain ability to acquire nutritionally adequate and safe food in socially acceptable ways” [30], [31]. We will use USDA 12-month Food Security Scale Questionnaire, one of the most widely use self-report questionnaires to measure food insecurity [19]. Given the high volume of questionnaire measures in this study, we opt to use the 6-item short-form version as this has been found to have reasonable sensitivity and specificity as compared to the full 18-item [32] with less burden to the participant (**APPENDIX E**).

5.2.12. Resource availability in childhood

Participants will complete a 3-item measure of perceived resource availability during childhood developed in 2011 by Griskevicius et al. [33] and used in previous studies investigating the relationship with obesity or eating behaviour [20], [21] (**APPENDIX F**).

5.2.13. Food choice motives

To assess food choice motives we will use the ‘Health’ (6 items, e.g. “Keeps me healthy”) and ‘Weight control’ (3 items, e.g. “Is low in calories”) subscales from the Food Choice Questionnaire [50]. These questions are rated from 1 (Not at all important) to 4 (Very important) (**APPENDIX G**).

5.2.14. Compensatory health beliefs

We will use two measures of compensatory health beliefs, forming a 7-item questionnaire (adapted from [51,52]). We will use the 3-item weight-regulation subscale developed by Knäuper and colleagues [51]. Participants rate from 1 (not at all) to 5 (very much) how much the compensatory health belief matches their own belief around weight regulation (e.g. “Eating dessert can be made

up for by skipping the main dish"). We will also use the 4-item portion size subscale developed by Poelman and colleagues [52]. Participants rate from 1 (not at all) to 5 (very much) how much the compensatory health belief matches their own belief around portion size (e.g. "If I eat a small meal, it's fine to have a larger portion during the next meal") (**APPENDIX H**).

5.2.15. Other questionnaire measures

We plan to collect some questionnaire items for the purpose of other research that will not be used in the present study (**APPENDIX I**).

5.2.16. Demographic and socioeconomic status measures

Participants will be asked to report their gender, age and ethnic group, employment status, and to report four measures of socioeconomic status:

- their highest educational qualification;
- their number of years in higher education;
- their household income and their household composition;
- a subjective measure of their socioeconomic status using the MacArthur Scale of Subjective Social Status (SSS) [34].

5.2.17. Study experience questionnaire

Aims guessing. Participants will be asked to report what they thought the aims of the study were in an open-ended response format.

Manipulation awareness. To assess awareness of the difference in portion sizes between the two study days, participants will be asked a series of questions with a yes/no response format about their experience of the study. The questions will consist of several filler questions to distract from the focus on portion size, and a single item to assess awareness of the portion size manipulation ("I noticed a difference in the size of the lunch and dinner portions between the two study days"). All the participants will also be asked to order the portion sizes (smallest and largest lunch and dinner portions) according to the study day (1 and 2) in which they were served.

Food liking. Participants will be asked to report how much they liked (from 1 [*not at all*], to 7 [*very much*]), each of the specific foods presented in the study.

Familiarity ratings. Participants will also be asked to indicate their agreement with the following statement, indicating familiarity with the foods served in the study: "I would normally eat this type of food" (rated from 1 [*strongly disagree*], to 7 [*strongly agree*]).

Normality ratings. Participants will be shown a picture of each portion size of the portion-manipulated lunch and dinner dishes and asked: "In your opinion, how normal is this portion? By 'normal' we mean whether the portion contains a normal amount of food to eat for a single meal." Responses will be collected on 7-point Likert scales ranging from 1 (not normal, it is far too small), to 7 (not normal, it is far too big), with a midpoint of 4 (normal).

5.2.18. Filler measures

Participants will complete mood ratings before and after eating each meal (on visual analog scales ranging from 0 – 100 with embedded 'hunger and fullness' ratings) and computerised tasks assessing categorisation of positive versus neutral words during the lunch session each day as part of the cover story. Participants will also complete a daily sleep quality questionnaire to distract from the focus on food intake.

Computerised mood task. The computerised mood filler task consists of a 1-minute lexical decision task. The task will be introduced as “A new way to assess mood by measuring speed of responding to positive versus neutral words”. Five positive words, 5 neutral words, and 5 ‘non-words’ will be presented on the computer screen one by one in a random order. Participants will be asked to respond to each word/non-word by pressing the left or right key marked on the keyboard to indicate whether the task displays a word or non-word (according to the key assignment specified in the task instructions). There will be two different versions of the task, each consisting of different word sets – one for each study day.

